A prospective randomized single blind controlled study on maintenance therapy with Sintilimab after radiotherapy and chemotherapy for locally advanced head and neck tumors based on peripheral blood CD8TEX detection

Main researcher: [name]

Plan version number: 1.0 version

Date of formulation: January 25, 2024

Main research unit: Second Affiliated Hospital of Zhejiang University

1. Introduction to research background:

Head and neck squamous cell carcinoma (HNSCC) includes cancers of the mouth, oropharynx, larynx and hypopharynx. The incidence rate ranks the sixth with a mortality rate of 40-50%. It is a serious disability and life-threatening disease. Due to the unique anatomical location, the surgical disability rate of HNSCC is high, which seriously affects the quality of life of patients. Radiation therapy is a very important local treatment for malignant tumors. Radiation therapy not only protects organ function and has cosmetic effects, but also has a long-term survival comparable to surgical treatment for early HNSCC patients receiving radiation therapy. However, over 60% of HNSCC patients are initially diagnosed as locally advanced. For patients with locally advanced stage who cannot undergo surgery, the current standard treatment regimen is synchronous radiotherapy and chemotherapy (CRT) or synchronous targeted treatment with cetuximab, followed by clinical follow-up. However, there are still relatively high rates of local recurrence or distant metastasis in patients with locally advanced head and neck tumors after radiotherapy and chemotherapy. The 3-year PFS rate is about 60%, 50% of relapses occur within 2 years after radiotherapy and chemotherapy, 20% to 30% of patients experience distant metastasis, and the overall 5-year survival rate is less than 50%. Therefore, it is necessary to further optimize the maintenance treatment plan after radiotherapy and chemotherapy, in order to improve the clinical cure rate of patients with locally advanced head and neck tumors.

Immunotherapy has achieved significant breakthroughs in recurrent and metastatic head and neck tumors. Studies on various tumor models have shown that tumor infiltration of PD-1+CD8+depleted T cells (CD8+TEX) is an important mechanism for the reduction of anti-tumor function and tumor progression in the body. Immunotherapy can reactivate T cell responses by blocking the PD-1 pathway. A

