At present, there are no research reports on the changes of CD8+TEX cells in the tumor immune microenvironment after radiotherapy. In our preliminary research, we found in the HNSCC mouse tumor model that the proportion and quantity of PD-1+CD8+TEX cells in the tumor and peripheral blood significantly increased with the prolongation of time after radiotherapy, and the combination of immunotherapy at the end of radiotherapy or 7 days after radiotherapy had the best therapeutic effect. We further tested the proportion of TEX in human peripheral blood and the expression level of PD1 during and after synchronous radiotherapy and chemotherapy, and found a similar trend as in the mouse model. So we speculate whether the proportion of peripheral blood CD8+TEX cells and the expression level of PD1 can be used as a suitable screening for immunotherapy. In the early stage, we retrospectively analyzed three patients who underwent immune maintenance therapy after synchronous radiotherapy and chemotherapy, and found that they have been followed up for three years, and no PFS time has been obtained. This study aims to ensure that patients receive standard treatment. By screening the proportion of CD8+TEX cells in peripheral blood and the expression level of PD1, patients with upregulation of CD8TEX in peripheral blood after radiotherapy or patients with PD1 expression levels higher than normal were randomly divided into two groups: one group received maintenance therapy for immunity, and the other group received placebo comparison to evaluate PFS time.

2. Research Purpose

2.1 Research Purpose:

A prospective randomized single blind controlled study on maintenance therapy with Sintilimab after radiotherapy and chemotherapy for locally advanced head and neck tumors

2.2 Main study endpoints:

Evaluation of progression free survival (PFS) and 1-year progression free survival (PFS) in two groups of patients with locally advanced head and neck tumors after radiotherapy and chemotherapy (using RECIST 1.1 criteria)

2.3 Secondary study endpoints:

Evaluation of overall survival (OS), safety and tolerability, changes in quality of life relative to baseline, and time to deterioration in maintenance therapy with Xindilimab in patients with locally advanced head and neck tumors after radiotherapy and chemotherapy (EORTC QLQ-C30 and H&N-35)

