This study is a prospective single blind randomized controlled clinical trial of maintenance therapy with Xindilimab based on peripheral CD8TEX screening after standard radiotherapy and chemotherapy for locally advanced head and neck tumors. Synchronous radiotherapy and chemotherapy are routine standard treatments and do not require the use of immunotherapy drugs in this study. Blood samples were collected before and after radiotherapy, and participants were screened and evaluated according to the inclusion and exclusion criteria of the protocol within 28 days before randomization. Patients who

agree to participate in this study will sign an informed consent form (ICF) prior to the screening process. After completing all screening activities, eligible participants can start receiving study treatment. According to the estimated sample size, a total of 104 patients are planned to be enrolled and randomly assigned equally to the experimental group and control group. The treatment cycle for the study is 21 days. The experimental group starts treatment within one month after the end of radiotherapy and chemotherapy. On the first day of each cycle, intravenous treatment with Sintilimab is given, with a cycle of 21 days. It is expected to be administered for a total of 18 cycles, or until the disease progresses; The control group received placebo treatment. The experimental group underwent routine blood tests, liver and kidney function, myocardial enzyme spectrum, thyroid function, electrocardiogram every 2 cycles, and CT scans every 4 cycles to evaluate toxic side effects; The control group underwent the same frequency of follow-up and observation. The study started on January 1, 2024 and ended on January 1, 2027, to explore the efficacy of maintenance therapy with Xindilimab after radiotherapy and chemotherapy for locally advanced head and neck tumors.

Research plan:

Intravenous infusion of Sintilimab, D1, once every 3 weeks

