3.4.3 Efficacy evaluation

Inspection items	Inspection time and related instructions
Imaging examination	Complete baseline assessment within 1 month before treatment, and treat every 3 months Chest and abdominal CT examination evaluation

3.4.4 Testing items and time after discontinuation/withdrawal from the study (once every 9 weeks since the last medication use)

Inspection items	Inspection time and related instructions
Telephone follow-up	Telephone follow-up every two months

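### The protocol does not secure tumour imaging after study drug stops, although the primary endpoints are PFS and 1-year PFS by RECIST 1.1

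*Protocol*

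**What the plan says.** - **Endpoint (Protocol 2.2).** "Evaluation of progression free survival (PFS) and 1-year progression free survival (PFS) in two groups of patients", with RECIST 1.1 as the criterion.
- **Design (3.3).** "CT scans every 4 cycles to evaluate toxic side effects", with the same frequency of observation in the control group. On treatment length: "It is expected to be administered for a total of 18 cycles, or until the disease progresses". On the study period: "The study started on January 1, 2024 and ended on January 1, 2027".
- **Efficacy imaging (3.4.3).** A baseline scan, then "treat every 3 months Chest and abdominal CT examination evaluation". The wording is garbled. It gives no end, such as progression or study end, and does not say whether the schedule depends on being on drug.
- **After stopping (3.4.4).** The heading covers the period "after discontinuation/withdrawal from the study (once every 9 weeks since the last medication use"). The single visible row is "Telephone follow-up every two months".
- **Suspension and permanent stopping (3.5.2, text after the table).** Efficacy imaging is kept on plan in two situations where drug is suspended for more than 12 weeks. Participants who stop permanently pass to follow-up, and imaging there is not mentioned.
- **Background (section 1).** "The 3-year PFS rate is about 60%, 50% of relapses occur within 2 years after radiotherapy and chemotherapy".

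**The concern.** RECIST progression cannot be established by telephone. The only schedule that starts from the last dose shows telephone contact and nothing else, so a site following it literally could stop scanning a participant who has not progressed. The protocol foresees such participants: the 3.5.2 table and the infusion-reaction guidance both require permanent stopping for certain toxicities, and completers reach the same point after cycle 18. An analysis plan can decide how to censor, but it cannot recover scans that were never made.

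Section 3.4.4 also puts stopping drug and leaving the study under one heading. A participant who stops for toxicity but remains willing to be followed is therefore not clearly distinguished from one who has withdrawn.

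**Working it through.** The plan gives no figure of its own on this point. The check has three parts.

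**1. Calendar, in days from first dose**
- CT every 4 cycles: 4 x 21 = 84, so days 84, 168, 252 and 336; the next would be day 420.
- CT every 3 months: the month-12 scan falls at about day 365.
- Dose of cycle 18: 17 x 21 = day 357 (11.73 months of 30.44 days). End of cycle 18: 18 x 21 = day 378.

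The clock in 3.4.4 starts at the last dose, so day 357 is the relevant cut-off. If 3.4.4 replaces 3.4.3, a completer's last 4-cycle CT is on day 336, and the 3-monthly scan at about day 365 and all later scans are unsecured.

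**2. PFS events after day 357 (illustration)**

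From the protocol: N = 104 and 3-year PFS of about 60%. Assumed: that figure applies from first dose to both arms pooled; uniform accrual over A = 12 to 24 months; data cut at 36 months. Three curves, each with F(36) = 0.40:
- Exponential: h = -ln(0.6)/36 = 0.01419 per month; F(11.73) = 0.1533.
- Relapsing fraction with a half-time of 24 months, which uses the background statement on relapse timing: p = 0.4/(1 - 2^-1.5) = 0.619; F(t) = p(1 - 2^(-t/24)); F(11.73) = 0.1778.
- Front-loaded Weibull, assumed shape 0.7: F(t) = 1 - exp(-0.04158 t^0.7); F(11.73) = 0.2078.

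Follow-up is at least 36 - 24 = 12 months for everyone, so events up to day 357 are 104 x F(11.73). Total events are 104 times the mean of F(36 - u) over entry times u from 0 to A. For the exponential this is 104 x [1 - (e^(-h(36-A)) - e^(-36h))/(hA)].

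| Curve | Total events (A = 12 / 24) | Up to day 357 | After day 357 | Share after |
|---|---|---|---|---|
| Exponential | 35.97 / 29.66 | 15.94 | 20.0 / 13.7 | 56% / 46% |
| Half-time 24 months | 37.16 / 31.53 | 18.49 | 18.7 / 13.0 | 50% / 41% |
| Weibull 0.7 | 37.58 / 32.74 | 21.62 | 16.0 / 11.1 | 42% / 34% |

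With the end of cycle 18 (day 378) as the cut-off, the range is 32% to 53%.

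**3. Early stoppers and the 1-year endpoint**

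The chance of an event between stopping at month s and month 12, if event-free at s, is [F(12) - F(s)]/[1 - F(s)].
- s = 3: 12.0% to 13.7% across the three curves, with three of the four 4-cycle CTs unscheduled.
- s = 6: 8.2% to 9.2%, with two unscheduled.

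The documents give no stopping rate. Assume 5% to 25% (5.2 to 26 participants), with stopping times uniform over months 0 to 9. The mean chance under the exponential curve is 1 - (e^(-3h) - e^(-12h))/(9h) = 10.0%. That gives 5.2 x 0.100 = 0.5 to 26 x 0.100 = 2.6 events in unscheduled time, against 104 x 0.1566 = 16.3 expected by month 12.

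**The case against.** The strongest reply is that 3.4.3 simply continues. It is an efficacy schedule separate from the dosing-linked checks in 3.4.2, it carries no stop date, and 3.4.4 does not say that it replaces it. Section 3.5.2 shows that imaging was not meant to follow every interruption of drug. This reading is possible. It does not remove the point, because 3.5.2 speaks only of suspension and nothing says that scans continue after permanent stopping or completion.

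A second reply is that the text at hand may be incomplete. Section 3.4.1 has a heading and no content, and the 3.4.4 heading announces testing items while only a telephone row is visible. A lost row is possible, so the source table should be checked before anything is changed.

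A third is that completers are covered at one year if treatment is taken to run to the end of cycle 18, since day 365 falls before day 378. That is fair, and even on the day-357 cut-off only about a week is at issue for the month-12 scan.

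A fourth is that 3.4.3, as visible, names chest and abdominal CT only. Extending that calendar would not by itself capture every locoregional progression. This limits what the fix recovers and is another reason to read the event shares as upper bounds.

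Stronger inferences are tempting but not supported:
- That the protocol ends imaging with treatment, so that PFS after about 12 months is compromised in everyone. This holds only if 3.4.4 replaces 3.4.3.
- That the background figure means only half of relapses come within two years. The protocol offers it as background on relapse and does not stress lateness.
- That ascertainment would differ between arms because of toxicity-driven stopping. This is plausible, but no stopping rates are given and it cannot be sized.

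**Conclusion.** The point holds as an unresolved gap in the protocol and should be fixed; confidence is medium because the source table may say more than the text at hand. The visible post-treatment schedule cannot establish the primary endpoint, and no passage says that imaging continues alongside it.

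If 3.4.4 replaces 3.4.3, roughly a third to just over half of PFS events (34% to 56%, or 11 to 20 of about 30 to 38) could fall after the last dose. Accrual, data cut and curve shape are assumed, and only the 3-year PFS of about 60% and N = 104 come from the protocol. The range is an upper bound on the loss, since deaths, and progression found in routine care, could still be reported by telephone. The effect on 1-year PFS is small, about 0.5 to 2.6 of 16 events under an assumed stopping rate, and mainly in early stoppers. The main exposure is overall PFS.

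**What to change.** First check the source tables for 3.4.3 and 3.4.4. If no imaging row is missing, then:
- State in 3.4.3 and 3.4.4 that participants who stop study drug for any reason other than progression, death or withdrawal of consent stay on the same 3-monthly imaging calendar. This applies in both arms, regardless of treatment status, at least through a scan at or just after one year.
- Separate stopping study drug from withdrawing from the study in 3.4.4.
- Reconcile the 4-cycle interval (84 days) with the 3-month interval (about 91 days), and the 9 weeks in the 3.4.4 heading with the two months in its row. The second is minor.

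The cost is an amendment to two short tables, a few added scans for early stoppers, and one scan near one year. Scans up to about month 12 are already planned for anyone who stays on treatment. Imaging beyond one year would protect overall PFS but costs more, so it is optional. How PFS is censored after the last scan can be left to the statistical analysis plan, which is not at hand.

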3.5 Treatment of subjects

3.5.1 Intervention measures

Sintilimab treatment regimen

drug	Dosage	Administration frequency	Usage method	treatment cycle
Sintilimab	According to the recommended dosage in the manual	Q3W	Intravenous infusion	Cycle every 21 days, administered on the first day

The use of Sintilimab (IBI308)

The main active ingredient of IBI308 is a recombinant human monoclonal antibody against programmed cell death receptor 1, with a concentration of 10 mg/mL. This product is a clear, colorless liquid, free from foreign objects, flocculent substances, and precipitates. The excipients include 140 mmol/L mannitol, 25 mmol/L histidine, 20 mmol/L sodium citrate dihydrate, 50 mmol/L sodium chloride, 0.02 mmol/L disodium edetate (ethylenediaminetetraacetic acid disodium), 0.2 mg/mL polysorbate 80, pH 6.0.

The minimum packaging unit for IBI308 is a box, with each box containing one injection of Sintilimab packaged in a penicillin bottle. The packaging box is printed with the drug name, dosage form, specifications, drug code, production batch number, expiration date, storage conditions, and information about the sponsor. The label of the penicillin bottle and the packaging box have the same information printed on them, but there is no information on the dosage form, precautions, and dosage on the penicillin bottle label. All packaging boxes and penicillin bottles are labeled as "for clinical research purposes only". The finished product of Sintilimab is stored in a dark place at 2-8 °C and has a shelf life of 24 months. If there are quality problems such as turbidity and precipitation in the injection, it should be immediately sealed and Xinda Biopharmaceutical (Suzhou) Co., Ltd. (hereinafter referred to as "Xinda Biotech") should be notified immediately.

The intravenous infusion time of IBI308 should be within 30-60 minutes. Do not administer

through intravenous injection or single rapid intravenous injection.

The guidance for dilution of drugs before administration is as follows:

- Solution preparation and infusion
- Do not shake the medicine bottle.
- Restore the medication bottle to room temperature (25 ° C or below) before use.
- After removing the medicine bottle from the refrigerator, it can be left at room temperature (25 ° C or below) for a maximum of 24 hours before dilution.
- Before administration, the injection medication should be visually inspected for the presence of suspended particles and discoloration. This product is a clear to slightly milky, colorless to light yellow liquid with no foreign objects. If visible particles are observed, the medicine bottle should be discarded.
- Extract 2 bottles of this product injection (200mg) and transfer them to an intravenous infusion bag containing 9mg/ml (0.9%) sodium chloride solution. Prepare a final concentration range of 1.5-5.0mg/ml. Gently flip the diluent and mix well.
- From a microbiological perspective, this product must be used immediately upon dilution and should not be frozen. The stability study of this product shows that it can be stored in dark at 2-8 ° C for 24 hours, including a maximum of 6 hours under indoor light at 20-25 ° C (6 hours including administration time). After refrigeration, the medication bottle and/or intravenous infusion bag must be restored to room temperature before use. The infusion tube used during infusion must be equipped with a sterile, heat free, low protein binding infusion tube filter (pore size 0.2) μ m). The infusion time is within 30-60 minutes.
- Do not use the same infusion tube to administer medication simultaneously with other medications.
- This product is for one-time use only. Any unused medication remaining in the medication bottle must be discarded.

Medication adjustment of Sintilimab

Throughout the entire research process, it is not allowed to adjust the dosage of Xindilimab. The principles of suspending and permanently stopping Xindilimab administration are shown in the table below.

3.5.2 信迪利单抗暂停给药和永久停药原则

Adverse events with Sintilimab	Severity	Dose adjustment
pneumonia	Grade 2	Suspend administration ^a
	Grade 3 or 4 or recurrent level 2	Permanent discontinuation of medication
Diarrhea/Colitis	Grade 2 or 3	Suspend
	Grade 4	Permanent
hepatitis	For subjects with normal baseline ALT, AST, or TBIL, level 2 AST, ALT (3-5 times ULN), or TBIL (1.5-3 times ULN) were elevated; For subjects with baseline AST, ALT, or TBIL>ULN, an increase of $\geq 50\%$ in AST, ALT, or TBIL (meeting level 2 requirements) and a duration of <7 days is required	Suspend administration ^a

	For subjects with normal baseline ALT, AST, or TBIL, grade 3 or 4 AST, ALT (>5x ULN), or TBIL elevation (>3x ULN); For subjects with baseline AST, ALT, or TBIL>ULN, AST, ALT, or TBIL increase $\geq 50\%$ (meeting level 3 or 4 requirements) and duration ≥ 7 days	Permanent discontinuation of medication
nephritis	Grade 2 or Grade 3 elevated blood creatinine	Suspend administration ^a
	Grade 4 elevated blood creatinine	Permanent discontinuation
Endocrine disorders	Symptomatic grade 2 or 3 hypothyroidism	Suspend administration ^a
	Grade 2 or 3 hyperthyroidism	
	Grade 2 or 3 pituitary inflammation	
	Grade 2 adrenal insufficiency	
	Grade 3 hyperglycemia or type 1 diabetes	Permanent discontinuation of medication
	Grade 4 hypothyroidism	
	Grade 4 hyperthyroidism	
	Grade 4 pituitary inflammation	
	3rd or 4th grade adrenal insufficiency	
Skin adverse reactions	Grade 4 hyperglycemia or type 1 diabetes	
	Grade 3	Suspend administration ^a
thrombocytopenia	Level 4, Stevens Johnson syndrome (SJS) or toxic epidermal necrolysis (TEN)	Permanent discontinuation
	Grade 3	Suspend
	Grade 4	Permanent

Other immune related adverse reactions	Level 3 or 4 elevated blood amylase or lipase	Suspend administration ^a
	Grade 2 or 3 pancreatitis	
	Grade 2 myocarditis c	Permanent discontinuation of medication
	Other immune related adverse reactions that occur for the first time at level 2 or 3	
	Grade 4 pancreatitis or any level of recurrent pancreatitis	
	Grade 3 or 4 myocarditis	
Recurrent or persistent adverse reactions	Grade 3 or 4 encephalitis	Permanent discontinuation of medication
	Other immune related adverse reactions that first occurred at level 4	
	Recurrent grade 3 or 4 (excluding endocrine disorders)	
	Grade 2 or 3 adverse reactions within 12 weeks after the last administration	
	Not improved to level 0-1 (excluding endocrine diseases)	Permanent discontinuation of medication
	Failure of corticosteroids to decrease to $\leq 10\text{mg/day}$ prednisone equivalent dose within 12 weeks after the last administration	

Table: Suspension and permanent discontinuation of Sintilimab regimen

a: Resumption of medication after symptom improvement to level 0-1 or baseline level.

b: Pituititis, adrenocortical insufficiency, thyroid insufficiency/hypothyroidism and type 1 diabetes can be reused when they are fully controlled and only need physiological hormone replacement treatment.

c: For abnormal results in Level 4 laboratory tests, the decision to terminate medication should be based on accompanying clinical symptoms/signs and the researcher's clinical judgment.

The maximum interval allowed for drug suspension is 12 weeks. If the subject cannot recover to a state where they can reuse Sintilimab within 12 weeks, they will permanently discontinue Sintilimab and enter the follow-up phase. Excluding the following two situations:

1) Due to the use of glucocorticoids in the treatment of irAE, the process of reducing glucocorticoids resulted in the suspension of Sintilimab for more than 12 weeks. In this case, it is

necessary to discuss with the medical manager of the sponsor to decide whether to continue treatment with Sintilimab. The imaging examination for evaluating the therapeutic effect is carried out according to the plan and is not affected by the suspension of medication.

2) Due to the treatment of AE unrelated to Xindilimab, Xindilimab was temporarily suspended for more than 12 weeks. In this case, it is necessary to discuss with the sponsor to decide whether to continue treatment with Sintilimab. The imaging examination for evaluating the therapeutic effect is carried out according to the plan and is not affected by the suspension of medication.

The principle of restoring Sintilimab

When resuming the use of Sintilimab, relevant AEs need to be restored to level 0-1 or baseline, with an ECOG PS score of 0-1.

Management of infusion reactions related to Sintilimab

Xindilizumab may cause severe or life-threatening infusion reactions, including severe hypersensitivity or allergic reactions. Signs and symptoms usually appear during or shortly after drug infusion, and can usually be completely resolved within 24 hours of completion of infusion.

The management guidelines for infusion reactions associated with Sintilimab are shown in Table 2.

NCI CTCAE classification	Treatment	Perform pre-treatment medication during subsequent administration
Grade 1 Mild reactions; No need to interrupt infusion; No intervention required	According to the patient's medical indications, strengthen monitoring of their vital signs until the researchers believe that the subject's condition is stable.	None


Grade 2
 
Treatment or interruption of infusion is necessary, but symptomatic treatment (such as antihistamines, nonsteroidal anti-inflammatory drugs [NSAIDs], anesthetics, intravenous infusion) should be carried out as soon as possible to quickly generate a response; Preventive medication should be taken for ≤ 24 hours
	
Stop infusion and monitor symptoms.
 
Other appropriate drug treatments may include, but are not limited to: intravenous antihistamines
 
NSAIDS
 
Acetaminophen anesthesia
 
According to the patient's medical indications, strengthen monitoring of their vital signs until the researchers believe that the subject's condition is stable.
 
If the symptoms improve within one hour after stopping drug infusion, the infusion can be restarted at 50% of the original infusion rate (such as reducing from 100 mL/h to 50 mL/h). Otherwise, medication should be suspended until symptoms improve, and subjects should receive pre-treatment medication before the next planned administration.
 
For subjects who still exhibit level 2 toxicity despite receiving sufficient pre-treatment medication, further study drug treatment should be permanently discontinued.
	
Subjects receiving anti-PD1/PDL1 monotherapy
 
Within 1.5 hours (± 30 minutes) prior to treatment, the following pre-treatment medications can be accepted:
 
Oral administration of 50 mg diphenhydramine (or equivalent dose of antihistamine).
 
Oral administration of 500-1000 mg of acetaminophen (or an equivalent dose of antipyretic).

---	--	--


Grade 3/4
 
Grade 3:
 
Long duration (i.e. failure to respond quickly after symptomatic medication and/or brief interruption of infusion); Symptom recurrence after initial improvement; Hospitalization is required due to other clinical sequelae such as kidney damage and lung infiltration
 
Grade 4:
 
Endangering life; Require vasopressor medication or ventilation support
	
Stop infusion.
 
Other appropriate drug treatments may include but are not limited to: adrenaline * * intravenous infusion antihistamines NSAIDS Acetaminophen anesthesia Oxygen boosting drugs Corticosteroids are used to strengthen monitoring of the patient's vital signs based on their medical indications, until researchers believe that the subject's condition is stable.
 
Hospitalization may be required for treatment.
 
**If an allergic reaction occurs, adrenaline should be used immediately.
 
Subjects should permanently discontinue further study drug treatment.
	
No subsequent administration

Appropriate first aid equipment should be equipped in the ward and physicians should be available at all times during medication administration.
 
For further information, please refer to the Common Terminology Standard for Adverse Events (CTCAE) version 4.03
 
(http://ctep.cancer.gov)
		

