3.4 Research Evaluation Plan

3.4.1 Baseline evaluation

3.4.2 Pre medication evaluation of treatment plan (starting from d1, once every 6 weeks, completed each time before administration)

Inspection items	Inspection time and related instructions
Physical examination, medical history	
Medical history collection
 
Physical examination items must include: heart rate, blood pressure, respiratory rate, body temperature, height, weight, and neurological examination
 
Emphasis should be placed on inquiring about possible adverse reactions of Sintilimab

Peripheral blood routine	
The blood routine test must include: red blood cell count (RBC), hemoglobin (Hb), white blood cell count (WBC), and white blood cell classification count (absolute neutrophil and lymphocyte counts are required), hematocrit (HCT), and platelet count (PLT).

Blood biochemical examination	
The blood biochemistry items must include: blood electrolytes (K Na Ca Mg Cl HCO3- is necessary), ALT, AST, γ - GT, total bilirubin, direct bilirubin, amylase, lipase, creatinine, urea T nitrogen, serum albumin, blood glucose

thyroid function	
Thyroid function items must include: T3, T4,

	fT3, fT3, TSH
urinalysis	Urine routine items must include: urine specific gravity (SG), urobilinogen (URO), occult blood (BLD), white blood cells (WBC), urine protein (PRO), urine glucose (GLU), bilirubin (BIL), ketone bodies (KET), urine red blood cells (RBC), and urine color (COL).
Electrocardiogram examination	Twelve lead electrocardiogram
Blood and tissue specimens for biomarker research	Before treatment and before each efficacy evaluation (blood samples)

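### For subjects with raised baseline liver tests, the hepatitis row holds sintilimab for a short grade 2 rise but assigns no action to a first grade 3 rise of the same duration

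*Protocol*

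**What the plan says.** The suspension and discontinuation table in Protocol Section 3.5.2 has one hepatitis row with two action cells, each divided by baseline liver status.

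- **Normal baseline.** Grade 2 elevations lead to suspension and grade 3 or 4 elevations to permanent discontinuation. Neither has a duration condition.
- **Baseline AST, ALT or bilirubin above ULN, suspension cell.** A rise of at least 50% is needed, qualified as "meeting level 2 requirements) and a duration of <7 days is required".
- **Baseline above ULN, permanent-stop cell.** A rise of at least 50% is needed, qualified as "meeting level 3 or 4 requirements) and duration ≥ 7 days".

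Section 3.5.1 rules out dose adjustment, so hold and stop are the only two actions available. Raised-baseline subjects are eligible: inclusion criterion 10 in Section 3.1 admits ALT or AST up to 2.5 x ULN without liver metastasis.

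Section 3.3 schedules "liver and kidney function, myocardial enzyme spectrum, thyroid function, electrocardiogram every 2 cycles", and Section 3.4.2 times the pre-medication checks as "starting from d1, once every 6 weeks, completed each time before administration".

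**The concern.** A toxicity table should respond at least as firmly to a worse event as to a milder one of the same duration. For raised-baseline subjects this row does not. The two cells differ in both grade and duration, so the combinations that cross over fall between them. The important one is grade 3 under 7 days: followed literally, the row holds the next infusion for a short grade 2 rise but does not order that hold for a short grade 3 rise. What is at stake is the safety of a subject who is due a PD-1 antibody with an ongoing grade 3 liver rise.

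**Working it through.** There is no stated figure to reproduce. The check sets the cells side by side and asks whether another provision fills the gap.

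**1. The hepatitis row for raised baseline, rise of at least 50%, first event**

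| Grade | Under 7 days | 7 days or more |
|---|---|---|
| 2 | Suspend | No action in this row |
| 3 | No action in this row | Permanent stop |
| 4 | No action in this row; footnote c leaves it to judgement at most | Permanent stop |

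Only in the under-7-days column does a milder grade have an ordered action that a worse grade lacks.

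**2. Other provisions that might cover grade 3 under 7 days**

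- The line for other immune-related reactions first occurring at level 2 or 3 (Section 3.5.2): hepatitis has its own row, so this line does not clearly apply.
- The recurrence line: it needs a recurrence, and this is a first event.
- The persistence line: it needs failure to improve within 12 weeks of the last dose.
- Footnote c: it addresses level 4 laboratory results only.
- Section 7.3: it asks for timely handling of adverse events generally and, for serious ones, leaves stopping or reducing to the researcher. It orders no hold.

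**3. Can the event occur in an eligible subject?** Assume the ULN multiples printed in the normal-baseline clauses also define grade here (grade 2 at 3-5 x ULN, grade 3 or 4 above 5 x ULN for ALT/AST). From a baseline of 2.5 x ULN, a 50% rise gives 2.5 x 1.5 = 3.75 x ULN, which is grade 2. A doubling gives 2.5 x 2 = 5 x ULN, and anything above that is grade 3. So it can occur.

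**4. How wide is the window?** "The treatment cycle for the study is 21 days". If a grade 3 rise began 7 or more days before the next dose, then by the dose day it has either lasted at least 7 days (permanent stop) or dropped below grade 3. The gap therefore affects a dosing decision only when onset falls in the last 7 of the 21 days, and the rise is still grade 3 at dosing.

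**5. What can scheduled tests show?** They are 2 x 21 = 42 days (6 weeks) apart. Of those 42 days, 42 - 7 = 35 lie 7 or more days before the test. A rise first seen at a scheduled test could have begun on either side of the 7-day line, so one result does not fix its duration. Placing an event in the short grade 3 cell needs other evidence, such as an unscheduled test.

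**6. Comparison within the table.** None of the six other named organ rows (pneumonia, diarrhea/colitis, nephritis, endocrine, skin, thrombocytopenia) uses a day count. Nephritis, the nearest row defined by a laboratory value, suspends for "Grade 2 or Grade 3 elevated blood creatinine" and stops for "Grade 4 elevated blood creatinine", with no gap between the grades. This does not make a day count wrong; it suggests that the gap was not intended.

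**The case against.** The strongest reply is that the affected case hardly arises. If a short grade 3 rise has already resolved to grade 0-1 or baseline, nothing remains to hold, since footnote a permits dosing at that level. If it is still ongoing, its short duration is provisional and may soon meet the stop condition. What remains is an ongoing, datable rise with a dose due in the same week. That stands, and it is why the point is minor.

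A second reply is that an investigator could use the line for other immune-related reactions, or read level 2 as a minimum, because the raised-baseline clause prints no upper limit. Both readings are possible in a translated document, and in practice most investigators would probably hold the drug. Neither is clear, however. Hepatitis has a dedicated row, the same cell describes grade 2 as a band for normal-baseline subjects, and grade 3 or 4 has its own cell.

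A third reply is that waiting 7 days before a permanent stop is reasonable when baseline is raised. I agree and do not criticise it. That reasoning supports a hold while waiting; it does not explain why none is ordered.

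Two stronger readings are tempting but unsupported:

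- A reader might infer that every scheduled liver test exposes subjects to the reversal. It does not: a rise first found at a scheduled test has unknown duration, and then grade 2 and grade 3 are equally unplaced.
- A reader might infer that the protocol offers no response at all to a short grade 3 rise. The documents support only the narrower statement that the hepatitis row assigns none and no other provision clearly does.

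**Conclusion.** The point holds as a minor patient-safety wording error, with medium confidence because it rests on a literal reading of a translated table. For raised-baseline subjects with a rise of at least 50%, the hepatitis row orders a hold for a short grade 2 rise and assigns no action to a first grade 3 rise of the same duration. The grade 2 rise of 7 days or more and the short grade 4 rise are secondary gaps in the same cells.

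Its reach is small. Section 3.3 plans 104 patients allocated equally, so 104 / 2 = 52 would receive sintilimab. Only those with raised baseline liver tests and a grade 3 rise starting in the week before a dose are concerned. The protocol gives no rate for either, so no subject count can be stated. The sample size, power and alpha do not change.

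**What to change.** Amend the two raised-baseline clauses of the hepatitis row, for a rise of at least 50%:

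- **Grade 2, any duration:** suspend.
- **Grade 3 or 4, not yet shown to have lasted 7 days (including unknown duration):** suspend and repeat liver tests.
- **Grade 3 or 4, lasting 7 days or more:** permanent discontinuation, as now.

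This needs a protocol amendment to two table cells. The downside is an occasional short dose hold and a repeat liver test. Sample size, scheduled visits and analysis are unaffected.
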